2.0 STUDY OBJECTIVES AND ENDPOINTS

2.1 Primary Objective

Group 1 (Safety): Healthy Volunteers. The initial phase of the study is designed to determine the safety of the study device in healthy volunteers without wounds. If there are no issues with tolerance, side effects, or adverse reactions in healthy volunteers, the second phase of the study will proceed with active wound care subjects.

For the purposes of this study, if two subjects experience an unacceptable adverse reaction warranting discontinuation of treatment in the opinion of the Investigators during the initial phase of the study, the study will be halted and the second phase (and the remainder of the initial phase, if applicable) will not be completed. Allergic reactions and infections at the bandage site will be considered unacceptable at any clinical severity; other adverse reactions will be deemed "unacceptable" by the Investigators on a case-by-case basis dependent upon clinical severity (App. A).

Group 2 (Efficacy): Wound Care Subjects. The second phase of the study is designed to determine the effectiveness of the study device in wound healing in subjects with active wounds (see Primary & Secondary Endpoints below).

[figure not shown]
2.2 Primary Endpoint

The primary endpoint for this study is wound healing (Group 2), as defined by the percent change in wound surface area (surface area is calculated in cm²) from baseline through the active treatment period. Specifically, wound care subjects will have the study device applied at baseline then re-applied two times per week for up to 4 weeks from the start of the active treatment period. Device reapplication will change to weekly when the principal or sub-investigator determines it is permissible or when a maximum of 4 weeks of treatment is reached. Device re-application will continue weekly until the wound is judged to be healed by the wound care practitioner or up to 3 months, whichever comes first. If after 2 consecutive months of treatment with the study device the wound does not exhibit healing, evidenced by a decrease in surface area (cm²), the subject will be returned to standard and established techniques of treatment consistent with the wound etiology.

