3.3 Expected Study Duration and Subject Participation

Group 1: The initial healthy volunteer safety study will last a total of 4.5 weeks. Healthy volunteers will wear the study device for 3 consecutive days (up to 72 hours), followed by weekly visits for 4 weeks of observation for tolerance, side effects, and/or adverse reactions.

For the purposes of this study, if 2 subjects experience an unacceptable adverse reaction warranting discontinuation of treatment in the opinion of the Investigators during the initial healthy volunteer phase, the study will be halted and Group 2 (and the remainder of the initial phase, if applicable) will not be completed. Allergic reactions and infections at the study device application site will be considered unacceptable at any clinical severity; other adverse reactions will be deemed "unacceptable" by the Investigators on a case-by-case basis dependent upon clinical severity (App. A).

Group 2: The wound care subjects will have twice per week study device applications to a specific ulceration for up to the first 4 weeks of treatment and then weekly reapplication thereafter. For subjects that exhibit any reduction in wound surface area, this application will occur until the wound is healed, or for up to 3 months (whichever occurs first). For subjects that do not exhibit any reduction in wound size at 2 months, application will stop and standard treatment protocols will be pursued. At the conclusion of the treatment window (up to 3 months), subjects will be followed every 3 months for 12 consecutive months for observation of late side effects or adverse reactions (3 months of active treatment, 12 months of follow-up observation, 15 months total).

IRB# 1331496 Page 19 Version 6.0

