- ♦ *Missed study follow-up visits:* Subjects who miss two consecutive follow-up visits will be contacted as described in section 5.12 in order to determine whether they wish to withdraw for the study or re-establish regular study follow-up visits. If subjects are able to re-establish study follow-up visits they may remain on the study. If the subject is unable to be contacted through the procedures outlined in section 5.12 data collection from the electronic medical record may continue, but the subject will be considered "lost to follow-up".
- ♦ Wound healing and discontinuation from study treatment: Clinical benefit may be determined during the treatment process by documentation of a healed ulceration, at which time the study device application will be discontinued. The post-treatment follow-up period will then begin for observation of late side effects and/or adverse reactions.
- ♦ *No evidence of wound healing at 2 months.* If a subject has no evidence of decreased wound surface area at 2 months (8 week treatment visit), the patient will be returned to standard and established techniques consistent with the wound etiology, and study follow-up will be discontinued.
- ♦ Wound < 50% healed at the completion of the study treatment period and discontinuation from study follow-up: If after 3 consecutive months (12 weeks) of treatment with the study device the wound does not exhibit at least a 50% decrease in surface area (cm²), the subject will be returned to standard and established techniques consistent with the wound etiology, and study follow-up will be discontinued. Clinical benefit experienced after the three-month treatment period, but not during the treatment period is not anticipated

In the absence of discontinuation due to adverse reactions (for both Groups 1 and 2) or wound healing outcomes (for Group 2 only) as indicated above, treatment may continue per the Schedule of Events (section 5.1) until one of the following criteria applies:

- ♦ Subject decision to withdraw from treatment (partial consent) or from the study (full consent),
- ♦ Death, or
- ♦ Funder reserves the right to temporarily suspend or prematurely discontinue this study.

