9.0 STATISTICAL CONSIDERATIONS

Primary Objective.

Group 1 (Safety): Healthy Volunteers. The initial phase of the study is designed to determine the safety of the study device in normal healthy volunteers without wounds. If there are no issues with tolerance, side effects, and/or adverse reactions in normal healthy volunteers, the second phase of the study will proceed with active wound care subjects.

Group 2 (Efficacy): Wound Care Subjects. The second phase of the study is designed to determine the effectiveness of the study device in wound healing in subjects with active wounds (see Primary Endpoint below), and to determine if the study device is equivalent to standard and established techniques (standard techniques demonstrate 50% wound healing at 2 months).

Primary Endpoint.

The primary endpoint for this study is wound healing (Group 2), as defined by the percent change in wound surface area (surface area is calculated in cm²) from baseline through the active treatment period. Wound care subjects will have the study device applied (and re-applied weekly) until the wound is judged to be healed by the wound care practitioner, for up to 3 months total duration. If after 2 consecutive months of treatment with the study device the wound does not exhibit at least 50% improvement in surface area (cm²), the subject will be returned to standard and established techniques consistent with the wound etiology. We will also determine if the study device is equivalent to standard and established techniques (standard techniques demonstrate 50% wound healing at 2 months).

Statistical Analysis Plan.

Descriptive statistics will comprise the bulk of the statistical analysis. Continuous variables will be reported as means and standard deviations, along with median and minimum/maximum values and compared between baseline and follow-up times using paired t-tests and/ or repeated measures ANOVA. Dichotomous and categorical variables will be reported as frequencies with percentages and compared between follow-up times using Chi-square tests or Kruskal Wallis tests. Imputation techniques will be used to account for missing data. Statistical significance will be set at p<0.05 for all the tests.

IRB# 1331496 Page 41 Version 6.0

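### The primary endpoint names no reading time, and the wound's own response decides when treatment ends, so percent change is read at outcome-dependent times and cannot be set against the 2-month benchmark

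*Combined protocol and SAP*

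**What the plan says.** Section 2.2 gives the primary endpoint as "percent change in wound surface area (surface area is calculated in cm²) from baseline through the active treatment period". Section 9.0 uses the same open window, "from baseline through the active treatment period". Neither names a week or a visit.

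The length of the window depends on the wound:

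- **Healing, or the maximum.** Treatment runs "until the wound is judged to be healed by the wound care practitioner or up to 3 months, whichever comes first" (2.2).
- **No response at 2 months.** Section 3.3 says: "For subjects that do not exhibit any reduction in wound size at 2 months, application will stop". Sections 2.2, 5.1 and 5.11 use the same criterion, no decrease in area. Section 5.11 ties it to the 8-week treatment visit and also ends study follow-up for these subjects.
- **A different 2-month rule.** Under the Primary Endpoint heading of section 9.0, subjects return to standard techniques if improvement is below 50% after 2 months.

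On analysis, section 9.0 offers paired t-tests and/or repeated measures ANOVA between baseline and follow-up times, without saying which time is primary. On missing values it says only: "Imputation techniques will be used to account for missing data". Group 2 has 10 subjects and no concurrent control. The only comparator is the benchmark of 50% healing at 2 months. Sections 2.3 and 2.4 treat that comparison as secondary, but section 9.0 also places it inside the Primary Endpoint paragraph.

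**The concern.** Taken as written, one subject's primary value may come from week 5 (healed), another's from week 8 (stopped for non-response) and a third's from week 12 (still improving). Wounds that shrink get up to four more weeks to shrink further, while wounds that do not are frozen at week 8. The average of such values belongs to no particular time after the start of treatment. It cannot be read against a 2-month figure, which is the only yardstick an uncontrolled study of 10 subjects has.

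The unspecified imputation adds to this. Subjects stopped at week 8 have no planned week 12 study measurement, and the reason is their outcome. If week 12 were chosen as the reading, a method that assumes values are missing at random could fill the gap from subjects who were improving. Because neither the reading time nor the method is fixed, both could be chosen after the data are seen.

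**Working it through.** The plan has no figure to reproduce: the 10 subjects come without a power, effect size or SD, and no healing rate is given. Every trajectory below is therefore my assumption. The reading times and stopping rules come from sections 2.2, 3.3, 5.1, 5.11 and 9.0.

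**Simple arithmetic.** Suppose a wound heals exactly at the benchmark, 50% smaller at 2 months. At 3 months, 1.5 times as long, its reduction is 1 - 0.5^1.5 = 65% if shrinkage is exponential, or 1.5 x 50% = 75% if linear. So an improving wound gains 15 to 25 points from the later reading alone.

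**Base case.** I simulated log-linear wound areas with the mean weekly rate set to 50% reduction at 8 weeks, between-subject SD 0.10 per week and visit noise 0.15 log units. A wound counted as healed below 5% of baseline, and no visits were missed.

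- No-decrease rule: mean change is about -38% at the last treatment reading and -29% at week 8, a gap of 9 points. If the baseline is taken as error-free, the figures are -39.0% and -30.2% (8.8 points).
- Under-50% rule of section 9.0, error-free baseline: about -36% versus -30% (5.9 points).
- Share of subjects with at least 50% reduction, no-decrease rule: 50% at week 8, 61% at the last reading.
- Week 12 without subjects stopped at week 8 (no-decrease rule): about -66%, against -26% for all subjects at week 12.

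**Other settings.** Across six settings of this model the last reading beat week 8 by 6 to 12 points under the no-decrease rule and by 4 to 8 under the under-50% rule. Outside that range:

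- With SD 0.03 to 0.05 at the same mean rate the gap is 12 to 14 points. The last reading is then within 0.2 point of a fixed week 12 reading, so nearly all of the gap is real later healing.
- With mean rate 0 and SD 0.03 it is about 0.5 point against the device.
- With mean rate 0.10 and SD 0.20 the week 8 mean is +64% while the median is -55%. A few growing wounds dominate the mean.

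**Allowing wounds to fluctuate.** A second model adds a weekly random walk. Entries are mean percent change. Where two values are given, the first is for the no-decrease rule and the second for the under-50% rule.

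| Assumed setting | Week 8, all | Last treatment reading | Week 12, all | Week 12, stopped subjects dropped |
|---|---|---|---|---|
| No average trend, wide spread | +16 | +14 / +15 | +34 | -36 / -69 |
| About 50% at 2 months, wide spread | -33 | -42 / -38 | -37 | -63 / -80 |
| Same median, narrower spread, more fluctuation | -38 | -47 / -41 | -51 | -60 / -72 |
| Slow healing with fluctuation | -20 | -24 / -20 | -29 | -41 / -60 |

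Three patterns follow:

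1. Against week 8, the last reading is 0 to 9 points more favourable here.
2. Against week 12 in all subjects, the sign changes. The last reading looks better in the first two rows and worse in the last two, where some stopped wounds would have improved later.
3. Dropping stopped subjects favours the device in every row, by 9 points (-60 versus -51) up to 103 points (-69 versus +34).

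**The case against.** A reader might infer that the primary endpoint is simply biased in the device's favour. The documents do not support that. They name neither the reading nor the imputation method, and against a fixed week 12 reading of everyone the sign reverses in two of the four fluctuating settings. Treatment of up to 3 months is part of the design, so a larger effect at 12 weeks than at 8 is not in itself bias. This objection stands, and the claim is limited accordingly.

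The benchmark comparison is assigned to the secondary endpoint in 2.3 and 2.4, and wounds are measured at every treatment visit, so week 8 values will exist for subjects still on treatment. This stands in part. Section 9.0 nevertheless puts the 2-month comparison inside the Primary Endpoint paragraph, and the 2.4 wording, within 2 months, does not fix a single visit either. Repeated measures ANOVA could use all visits, but no primary time or contrast is stated.

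If the endpoint is the last treatment reading, a subject stopped at week 8 has a value and nothing is missing because of stopping. That is correct. The imputation problem arises only if week 12 or another later time is the reading, and the plan does not exclude this. Nor does it say that values after stopping will be imputed, so this is a risk left open, not a stated intention.

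Lastly, this is a small first-in-human study with mainly descriptive analysis. That lowers what is expected of the inference, but a descriptive summary of the primary endpoint still needs a stated time.

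**Conclusion.** The point holds in this form. The primary reading time is undefined, treatment length depends on the outcome, and section 9.0 contradicts sections 2.2, 3.3, 5.1 and 5.11 on the 2-month rule, so the length of the active treatment period is itself unclear. The resulting percent change has no fixed meaning in time and is not comparable with 50% healing at 2 months.

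Relative to week 8, reading at the last treatment visit typically flatters the result by about 4 to 12 points. The extremes were half a point against the device, with no average healing, and 14 points in favour, with little variation between subjects. The one consistently large distortion, about 40 points in the base case, would come from a week 12 analysis or a missing-at-random imputation that rests only on subjects still on treatment. The imputation itself was not simulated; the 40 points are from dropping stopped subjects.

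The structural defect can be read from the text. The sizes rest entirely on assumed trajectories, since the documents give no rates or SDs. No general statement about direction against week 12 is warranted.

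**What to change.** In sections 2.2 and 9.0:

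- Define the primary endpoint as percent change in wound area from Day 0 to the week 8 visit in every treated subject. Section 5.11 already names that visit, it matches the benchmark, and both versions of the 2-month rule act at about that time, so the reading does not depend on which is kept.
- Count wounds judged healed before week 8 as 0 cm² (-100%) unless reopening is documented, and state this as an assumption. These subjects move to 3-monthly follow-up (5.9), so no week 8 measurement is scheduled for them.
- Replace the open-ended imputation sentence with one rule for a missing week 8 area, for example the last measured area, with a sensitivity analysis. Count such subjects as not reaching 50% for section 2.4.
- Report the median beside the mean.
- Report week 12 or last-treatment change as secondary, labelled as depending on response.
- Reconcile the 2-month rule in section 9.0 with sections 2.2, 3.3, 5.1 and 5.11. Which version is right is for the investigators to decide.

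The cost is a small wording amendment to both protocol and SAP, because 2.2 is protocol text. No visits are added. The price is that the headline figure leaves out weeks 9 to 12 and will probably be less favourable. A week 12 primary reading is possible instead, but stopped subjects would then have to go on being measured.

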2.3 Secondary Objective (Group 2 only)

Group 2 (Efficacy): Wound Care Subjects. The secondary endpoint of the study is to determine if the study device is equivalent to standard and established techniques (standard techniques demonstrate 50% wound healing at 2 months) in subjects with active wounds.

[figure not shown]
IRB# 1331496 Page 17 Version 6.0

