	Group 2 (Efficacy): Wound Care Subjects. The second phase of				
	the study is designed to determine the effectiveness of the study				
	device on wound healing in subjects with active wounds (see				
	Primary Endpoint below), and to determine if the study device				
	is equivalent to standard and established techniques (standard				
CELIDA DEGLOS	techniques demonstrate 50% wound healing at 2 months).				
STUDY DESIGN	This study is a prospective, interventional, non-randomized,				
	sequential phase study designed to assess the safety and				
	efficacy of the Noxsano Bandage (study device) in subjects				
	with a diabetic lower extremity ulceration and/or arterial				
CLIPATECE	insufficiency lower extremity ulceration.				
SUBJECT	Group 1: Initial subjects will be limited to healthy volunteers				
POPULATION	without wounds. Five (5) white subjects and 5 black or African				
	American subjects will be enrolled to evaluate skin differences.				
	Group 2: Ten (10) wound care subjects with lower extremity				
NUMBER OF	ulceration attributed to diabetes and/or arterial insufficiency.				
NUMBER OF	20 subjects will be included in the analysis (10 healthy				
SUBJECTS	volunteers for Group 1, and 10 active wound care subjects for				
NUMBER OF STEES	Group 2).				
NUMBER OF SITES	One site located at Riverside Methodist Hospital.				
PRIMARY	The primary endpoint for this study is wound healing (Group				
ENDPOINT	2), as defined by the percent change in wound surface area				
	(surface area is calculated in cm ²) from baseline through the				
CIDICALOU	active treatment period.				
SUBJECT FOLLOW-					
UP	total of 4.5 weeks. Healthy volunteers will have the study				
	device applied for 3 consecutive days (up to 72 hours),				
	followed by weekly visits for 4 weeks of observation for				
	tolerance, side effects, and adverse reactions.				
	Group 2 : The wound care subject treatment period will consist				
	of up to 3 consecutive months of study device application to a				
	specific ulceration. The study device will be changed two times				
	per week for up to 4 weeks from the start of treatment and then				

IRB# 1331496 Page 5 Version 6.0

	weekly for the remainder of the study treatment period. At the			
	conclusion of the treatment period, subjects will be followed			
	every 3 months for 12 consecutive months for observation of			
	late side effects and/or adverse reactions (up to 3 months of			
	active treatment, 12 months of follow-up observation, 15			

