2.4 Secondary Endpoint (Group 2 only)

Standard wound healing techniques generally demonstrate 50% wound healing at 2 months. Therefore, the secondary endpoint for this study is the proportion of wound care patients that have at least 50% improvement in surface area within 2 months of treatment. This information will be used to describe if the study device is equivalent to standard and established techniques.

IRB# 1331496 Page 18 Version 6.0

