5.11 Subject Withdrawal or Discontinuation

Subjects have the right to withdraw from the study at any time and for any reason without penalty or loss of benefits to which the subject is otherwise entitled. If a subject decides to withdraw, all study assessments, tests, and procedures will be stopped. An exit interview will be requested to understand why the subject chose to withdraw. The subject will also be offered the option to have data collection from the electronic medical record to continue in order to track wound progression. The Investigators may withdraw the subject at any time to protect the health, safety, or welfare of the subject. At the last point of contact, the date and reason for discontinuation will be documented, and every effort should be made to follow-up the status of any ongoing adverse events prior to withdrawal.

[figure not shown]
Subjects that do not present for the initial Noxsano Bandage application appointment will be withdrawn from the study and replaced.

Study participation may continue per the Schedule of Events (section 5.1) until one of the following criteria applies:

Group 1:

♦ Unacceptable adverse reactions warranting discontinuation of treatment in the opinion of the Investigators: Subjects experiencing any allergic reaction or infection at the device application site will be removed from study treatment.

IRB# 1331496 Page 29 Version 6.0

Group 2:

- ♦ Unacceptable adverse reactions warranting discontinuation of treatment in the opinion of the Investigators: Subjects experiencing any allergic reaction or infection at the device application site will be removed from study treatment.
- ♦ *Missed weekly treatment visits and discontinuation from study treatment*: Weekly treatment visits will be indicated as "missed" if the deviation from the planned date is > 2 days (i.e., 3 or 7 days ± 2 days, during the 3 month study period). If a subject misses 2 consecutive treatment visits, they will be removed from study and not replaced.

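### The plan promises to determine equivalence to standard care from 10 uncontrolled subjects, with no margin, no decision rule and no standard-care responder proportion

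*Combined protocol and SAP*

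**What the plan says.** **The aim.** Section 2.3 says: "The secondary endpoint of the study is to determine if the study device is equivalent to standard and established techniques". The objectives in the Protocol Summary carry the same promise. Section 9.0 makes it under Primary Objective and again under Primary Endpoint: "We will also determine if the study device is equivalent to standard and established techniques". Section 2.4 is softer: "This information will be used to describe if the study device is equivalent to standard and established techniques". The aim is therefore secondary in 2.3 and 2.4 but sits under primary headings in 9.0.

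**The measure.** Section 2.4 defines it as "the proportion of wound care patients that have at least 50% improvement in surface area within 2 months of treatment". The only comparator is a statement that standard techniques show 50% healing at two months.

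**The design and analysis.** Sections 3.1 and 3.2 describe a non-randomized study with 10 wound care subjects and no control group. Section 9.0 is mainly descriptive. For this type of variable it says: "Dichotomous and categorical variables will be reported as frequencies with percentages and compared between follow-up times". The significance level is 0.05 for all tests.

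**Missing subjects.** The Summary plans to include 10 Group 2 subjects in the analysis. Section 5.11 says: "If a subject misses 2 consecutive treatment visits, they will be removed from study and not replaced". Section 9.0 adds: "Imputation techniques will be used to account for missing data". No method is named.

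**The concern.** An equivalence statement needs three things: a comparator value on the same scale as the endpoint, a margin, and a rule linking data to conclusion. The plan supplies none of them.

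The endpoint is a proportion of patients. The benchmark is a healing percentage. Section 5.11 treats a wound less than 50% healed as one with less than a 50% decrease in area (at 12 weeks), so the benchmark most naturally matches the threshold that defines a responder. On that reading, no standard-care responder proportion is left to compare with. If it instead means that half of wounds heal, it describes a different event from the endpoint.

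Nothing in section 9.0 compares the observed proportion with any outside value. The 0.05 level belongs to tests of difference, and failing to find a difference is not evidence of equivalence. Followed as written, the plan ends in an equivalence statement with no criterion behind it, so the same count could be reported either way.

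**Working it through.** The plan gives no power, margin or responder rate, so there is no figure of its own to reproduce. The core point needs no arithmetic. The figures below show what 10 subjects could support.

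**Inputs from the documents:** n = 10 (section 3.2); endpoint a proportion (section 2.4). **Assumptions, not in the documents:** a standard-care responder proportion p0, a margin m, and the usual rule that equivalence is shown when the 90% interval lies within p0 ± m (two one-sided 5% tests).

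**Interval.** Clopper-Pearson for x of n: L = Beta quantile(α/2; x, n − x + 1) and U = Beta quantile(1 − α/2; x + 1, n − x).

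| Responders | 90% interval | 95% interval |
|---|---|---|
| 4/10 | 15.0–69.6% | 12.2–73.8% |
| 5/10 | 22.2–77.8% | 18.7–81.3% |
| 6/10 | 30.4–85.0% | 26.2–87.8% |

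**Smallest margin a result can meet:** m(x) = max(p0 − L, U − p0), using the 90% interval.

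With p0 = 50%:
- 5/10: max(50.0 − 22.2, 77.8 − 50.0) = 27.8 points.
- 4/10: max(50.0 − 15.0, 69.6 − 50.0) = 35.0 points; 6/10 is the mirror image.
- Other counts are worse, so the floor is about 28 points.
- At a 30-point margin only 5/10 passes. Its probability at a true 50% is 252/1024 = 24.6%.
- At 35 points, 4 to 6 of 10 pass, narrowly: (210 + 252 + 210)/1024 = 65.6%.

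With other assumed benchmarks, taking the best result in each case:
- 10%: 0/10 (90% interval 0–25.9%) gives max(10.0, 15.9) = 15.9 points; 90% is the mirror image.
- 20%: 1/10 (0.5–39.4%) gives max(19.5, 19.4) = 19.5 points; 80% is the mirror image.
- 30%: 2/10 (3.7–50.7%) gives max(26.3, 20.7) = 26.3 points; 70% is the mirror image.
- Across 30% to 70%, in steps of 0.5 points, the floor runs from 26.2 to 31.3 points.
- The floor dips lowest near 13% (and 87%), where 0/10 gives max(13.0, 25.9 − 13.0) = 13.0 points. That margin is as large as the benchmark itself.

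**One-sided reading (at least as good as standard care), p0 = 50%.** This is kinder. The one-sided 95% lower bound for 6/10 is 30.4%, which clears a 20-point margin (30%); P(X ≥ 6) at a true 50% is 37.7%. For a 10-point margin (40%), 7/10 falls short at 39.3% and 8/10 passes at 49.3%; P(X ≥ 8) is 5.5%. The plan states neither reading.

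**Early removals.** Suppose 2 of 10 are removed and 5 respond. Counting all 10 gives 5/10 = 50% (95% interval 18.7–81.3%). Counting only those measured gives 5/8 = 62.5% (24.5–91.5%). Imputation could give something else again, depending on the method.

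**The case against.** **The study is a small first-in-human pilot and mainly descriptive.** This is fair. Section 2.4 says the result will describe equivalence, section 9.0 puts most weight on descriptive statistics, and no equivalence test is planned. The practical risk is an unsupported sentence in a report, not a wrong formal test decision. But the Summary, 2.3 and 9.0 still promise to determine equivalence, so the descriptive intent does not remove the problem.

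**The denominator is given.** A reader might infer that the denominator is simply unstated. The documents do not support that: the Summary plans 10 Group 2 subjects in the analysis, and with imputation of missing values a natural reading is n = 10. What is missing is a specific rule for subjects removed early. The 5/8 figure illustrates that gap; it is not an equally supported reading.

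**The size rests on assumptions.** This also stands. The benchmark, margins and 90% rule are all supplied here, and the 26-to-31-point range holds only for benchmarks of 30% to 70%. A reader might also infer that a non-significant difference will be taken as equivalence. With 2 to 8 of 10 non-significant against 50%, a device with a true 25% rate would then pass 75.6% of the time. The plan proposes no such rule, so this is no measure of its error rate.

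**Conclusion.** The point holds. The plan promises an equivalence conclusion that 10 uncontrolled subjects, without a margin, a decision rule or a comparable benchmark, cannot support. The 95% interval of 18.7% to 81.3% for 5/10 rests only on n = 10. The 28-point floor adds an assumed 50% benchmark and two-sided equivalence; the floor is smaller at extreme benchmarks.

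A reader might infer that the trial is too small for its purpose. The documents do not show that: ten subjects can serve descriptive estimation, and the primary endpoint, percent change in wound area, is not affected by this point. The text should be changed to match the design.

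**What to change.** In the Summary, 2.3, 2.4 and 9.0:
- Replace the equivalence objective with estimation of the proportion of subjects with at least a 50% area reduction within two months, with an exact Clopper-Pearson 95% interval.
- State that equivalence will not be claimed, and quote the 50% healing figure as context only.
- List the aim as secondary throughout.
- Define the denominator as all Group 2 subjects who received the device. State that, for this endpoint, subjects removed early without a recorded reduction of at least 50% count as non-responders, in place of the imputation in 9.0. This is a defensible convention, not something the documents require, so the change should be explicit.
- State whether measurements from the electronic record count, since 5.11 allows that collection to continue for some subjects who withdraw or are lost to follow-up.
- Show alongside it the proportion among subjects with a two-month measurement.

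**Cost.** Text changes only, with no added subjects or visits. The sponsor gives up an equivalence statement, and the reported proportion may be lower.

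**Alternative.** Keeping equivalence would need a sourced responder proportion, a justified margin, a decision rule and a matching sample size. With an assumed 50% benchmark and 80% power at true equality, an exact two one-sided test needs about 53 subjects for ±20 points and 214 for ±10.

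**Separate matter.** The two-month criterion for return to standard treatment differs between sections 2.2, 3.3, 5.1 and 5.11 (any decrease in area) and 9.0 (at least 50%). Those sections must be reconciled.
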